3.1	2023-08-03	
 - Update of references to Global Safety Intake Form - Addition of Section 19 to include the addenda - Update of Addendum 10 and 11 (CIOMS form and Adverse Event Reporting Form)
3.2	2024-01-30	
 - Addition of Table of Content - Signature page: Name UZ Ghent investigators removed
3.3	2024-05-01	
 - AST test is no longer required
4.0	03/02/2025	
 - Use of new protocol template to ensure all needed sections are included. - make the document CTR compliant - Update contact information manufacturer blinded methotrexate - define MSD/Merck as distributor of Golimumab up until 30th of September 2024. - Update of Addendum 10 and 11 (CIOMS form and Adverse Event Reporting Form) - Removed stratification into groups of <3 months symptom duration and ≥3 month and <12 months symptom duration which has an impact on the sample size calculation. A sample size of at least 45 patients in each group is sufficient to obtain 80% power or more to detect a difference in proportions of 30% (20% versus 50%) at the alpha level of 5% using a Fisher's exact test.
5.0	03/04/2025	
 - Reference to the investigators brochure was removed. - Storage period biological samples is 10 years - Contraceptives must be used up until 6 months after last dose. - Donation of eggs (ova, oocytes) or sperm is not allowed during the study and for 6 months after the last dose of the study drug.
5.1	04/06/2025	
 - Administrative correction

Table of contents

Inhoud

Protocol modification history	2
Table of contents	4
List of abbreviations	7
Part I: Trial-related part of the protocol	9
1 Title of the trial	9
2 Trial number	9
3 General information	9
3.1 National Coordinating Investigator(s)	9
3.2 Sponsor	9
3.3 Departments/laboratories involved in the study	10
4 Introduction	10
4.1 Rationale + Background	10
4.2 Risk/Benefit assessment	11
4.3 Patient participation in trial design	12
5 Objective(s) of the study	12
5.1 Main objectives	12
5.2 Secondary objectives	13
6 End points	15
6.1 Primary end points	15
6.2 Secondary end points	15
7 Trial Design - The present study	17
7.1 Study design description	17
7.2 Start of the trial	22
7.3 End of the trial	22
7.3.1 For an individual subject	22
7.3.2 For the whole trial	22
7.4 Trial duration	22
7.4.1 For an individual subject	23
7.4.2 For the whole trial	23

4.1 Rationale + Background

Treatment of immune-mediated inflammatory diseases, such as SpA, with cytokine-directed bDMARDs, such as TNFi, has led to a revolution in the short and long-term control of symptoms, the improvement of quality of life and the prevention of irreversible structural damage. However, when started in the chronic phase of the disease (usually after failure of csDMARDs), these drugs need to be administered continuously, which in turn is associated with a major cost in healthcare expenditure (not only because of chronic treatment costs, but also as a consequence of the management of potential long-term side effects). The results of the proof-of-concept CRESPA trial suggest that by treating patients earlier, we can reach a state of sustained remission in which no long-term continuation of expensive drugs with potentially severe side effects is needed.

The SPARTACUS project aims to compare (cost-)effectiveness of inducing clinical remission in early forms of pSpA with a TNFi versus the current treatment paradigm with csDMARDs. Based on the preliminary CRESPA-trial-evidence, that intensive treatment in early phases of pSpA, is able to induce remission, we will also discontinue (biological) treatment in the second phase of this randomized, controlled clinical trial, once patients have achieved a status of sustained clinical remission; this will allow us to evaluate the possibility of drug-free remission. The time frame by which induction of drug-free remission is achievable is currently unclear. Therefore, we will analyse treatment responses in function of symptom duration (effect of symptom duration as a continuous variable, comparison between <3 months versus between 3 and 12 months). An additional unique feature of SPARTACUS project is the search of new biomarkers using state-of-the-art technologies both in synovial tissue and/or peripheral blood. Their ability to predict drug-free remission will be assessed in order to identify patients that may benefit from such an early induction therapy. The effect of improved patient selection and the potential better cost-effectiveness of intensive management of early pSpA will be estimated. Collectively, SPARTACUS should pave the path towards converting chronic lifelong therapy into a temporary intervention, which would result in a major societal impact on health and wealth.

References:

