5.1 Main objectives

The SPARTACUS study will explore the therapeutic efficacy of 2 different treatment strategies for patients suffering from peripheral Spondyloarthritis (pSpA), classified according to the “Assessment in SpondyloArthritis international Society” (ASAS) classification criteria (1) (see Addendum 1); it will be set up as a 48-week, prospective, randomized, active-comparator controlled, double-blind, double-dummy, clinical trial with a two-fold clinical objective:

- To compare a standard step-up approach using conventional synthetic Disease-Modifying Anti-Rheumatic Drugs (csDMARDs), such as methotrexate and/or sulphasalazine (the “csDMARD Step-Up”-strategy), with an early remission-induction treatment strategy that immediately introduces biological DMARDs (bDMARDs) as the first step in the treatment algorithm; in this group the Tumor Necrosis Factor inhibitor (TNFi) golimumab will be utilised (the “TNFi Induction”-strategy).

The double-blind phase of the study will compare the 2 treatment strategies with regard to the proportion of patients that achieve a status of (sustained) clinical remission.

In patients that reach sustained clinical remission, all study treatments (both in the “csDMARD Step-up”-group and the “TNFi Induction”-group) will be stopped, and long-term, clinical follow-up of these patients will allow to explore the possibility of “drug-free remission”; also with regard to this objective, the difference in symptom duration will be evaluated.

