In the CRESPA trial, we observed that despite the fact that 53% of patients were able to achieve drug-free remission, a significant proportion nevertheless relapsed. In this small proof-of-concept study, we were not able to detect significant predictors or remission or relapse. Also, 18% of patients did not achieve sustained clinical remission, but nevertheless experienced a significant improvement of signs and symptoms; in these patients long-term treatment was necessary. These results indicate that clinical response to TNFi is heterogeneous and underscores the need for biomarkers that can identify at baseline different pathogenic subsets that are associated with the (lack of) response to a TNFi. The recent introduction of new procedures such as ultrasound-guided synovial biopsy sampling in our early arthritis clinic has permitted to access synovial samples of virtually all peripheral joints (incl. wrists and small finger joints). By using innovative and unbiased tools recently developed in the area of single-cell analyses (RNA-sequencing and epigenetic profiling) by VIB and KU Leuven, we will obtain profound insights into the cellular heterogeneity of these unique patient samples.

4. To determine health-economic and societal impact of early, intensive bDMARD treatment of patients with recent-onset pSpA (compared to the currently reimbursed csDMARD Step-up strategy).

A unique feature of SPARTACUS is that clinical trial and biomarker discovery will be coupled to calculation of the health-economic benefits of such an approach. We aim to determine from a healthcare and a societal perspective, the 2 years’ cost-utility, as well as a model-based lifelong incremental cost-utility of the innovative strategy compared to usual care. Uncertainty analyses will be performed and budget impact for the Belgian healthcare and social security (work disability) system will be calculated by Maastricht University. Consistent with the increased call for transparency in health economic modelling, we aim to make our model available as a semi-open source model.

5. To increase awareness among referring physicians (general practitioners, other specialties that may evaluate patients with early SpA) and patient-advocacy groups about the value of early recognition and treatment in rheumatology.

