6.1 Primary end points

The primary endpoint of the study will be the comparison between the 2 treatment strategies at week 24 with regard to achievement of clinical remission (defined as complete absence of arthritis, dactylitis or enthesitis on clinical examination). At the week 24 timepoint, there are 3 possible scenario's (figure 3):

1. In patients that do not reach a state of clinical remission at week 24, blinded study medication will be interrupted and all patients will start open-label SC golimumab for an additional 36 weeks (up to max. week 60).
2. In patients that achieve sustained clinical remission at week 24, defined as absence of clinical arthritis, enthesitis and dactylitis at both week 12 and week 24, all study medication will be discontinued and prospective follow-up will be planned in SPARTACUS Phase B.
3. In patients that reach a state of clinical remission at week 24, but that did not yet reach this status at week 12, blinded study medication will be continued without any change in the treatment schedule for another 12 weeks.

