6.2 Secondary end points

In addition to this, several secondary endpoints will be evaluated:

- Comparison between the “TNFi induction” group and the “csDMARD Step-up” group regarding:
 - o Achievement of “sustained clinical remission” at week 24 (and week 36 for the patients remaining on blinded study medication).
 - o Improvement from baseline to week 12 and 24 in individual clinical assessments (78-Tender Joint Count, 76-Swollen Joint Count, Dactylitis Count, SPARCC Enthesitis Score) and composite scores (ASDAS: Axial Spondyloarthritis Disease Activity Score).

- Improvement from baseline to week 12 and 24 in patient-reported outcomes (Patient global assessment of disease activity and pain, BASDAI, BASFI, ASAS Health Index).
- Improvement from baseline to week 12 and 24 in inflammatory parameters (ESR, CRP).
- Changes in concomitant NSAID intake (NSAID-index) and “escape” intra-articular glucocorticoid injections between baseline and week 24
- Difference in occurrence of (serious) adverse events (AEs) and AEs of specific interest between the 2 treatment strategies from baseline to week 24 (and week 36 for patients remaining on blinded study medication). Descriptive analysis of the number and type of adverse events between both strategies
- Percentage of patients achieving (sustained) clinical remission with open-label golimumab treatment after failure of the initial randomized, blinded treatment strategy.
- Exploration of difference in percentage of patients that reach (sustained) clinical remission according to symptom duration (<3 months versus ≥3 month and <12 months). The interaction between treatment group and symptom duration as a continuous predictor will also be analyzed to investigate the effect of symptom duration with regard to reaching the specified primary and secondary outcomes.
- For patients in SPARTACUS Phase B (drug-free remission period):
 - Exploration of the duration of drug-free remission.
 - Time to (documented) pSpA disease flare.
 - Time to restart of “standard-of-care” pSpA treatment.
 - Exploration of clinical parameters that could be predictive for reaching (sustained) clinical remission and/or flare.
- Correlation between the “Patient Acceptable Signs & Symptoms Improvement” (“PASSI”) and different clinical assessments, laboratory values and patient-reported outcomes (or combinations thereof).

7 Trial Design - The present study

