- Improvement from baseline to week 12 and 24 in individual clinical assessments (78-Tender Joint Count, 76-Swollen Joint Count, Dactylitis Count, SPARCC Enthesitis Score) and composite scores (ASDAS: Axial Spondyloarthritis Disease Activity Score).
- Improvement from baseline to week 12 and 24 in patient-reported outcomes (Patient global assessment of disease activity and pain, BASDAI, BASFI, ASAS Health Index).
- Improvement from baseline to week 12 and 24 in inflammatory parameters (ESR, CRP).
- Changes in concomitant NSAID intake (NSAID-index) and “escape” intra-articular glucocorticoid injections between baseline and week 24
- Difference in occurrence of (serious) adverse events (AEs) and AEs of specific interest between the 2 treatment strategies from baseline to week 24 (and week 36 for patients remaining on blinded study medication). Descriptive analysis of the number and type of adverse events between both strategies
- Percentage of patients achieving (sustained) clinical remission with open-label golimumab treatment after failure of the initial randomized, blinded treatment strategy.
- Exploration of difference in percentage of patients that reach (sustained) clinical remission according to symptom duration (<3 months versus ≥3 month and <12 months). The interaction between treatment group and symptom duration as a continuous predictor will also be analyzed to investigate the effect of symptom duration with regard to reaching the specified primary and secondary outcomes.
- For patients in SPARTACUS Phase B (drug-free remission period):
 - Exploration of the duration of drug-free remission.
 - Time to (documented) pSpA disease flare.
 - Time to restart of “standard-of-care” pSpA treatment.
 - Exploration of clinical parameters that could be predictive for reaching (sustained) clinical remission and/or flare.
- Correlation between the “Patient Acceptable Signs & Symptoms Improvement” (“PASSI”) and different clinical assessments, laboratory values and patient-reported outcomes (or combinations thereof).

14 Data handling

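### Section 4.1 would identify who may benefit from early TNFi induction by whether a biomarker predicts drug-free remission, which cannot separate benefit over step-up from prognosis

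*Protocol*

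**What the plan says.** Section 4.1 (Rationale + Background) gives the purpose of the biomarker work: "Their ability to predict drug-free remission will be assessed in order to identify patients that may benefit from such an early induction therapy". The next sentence states the use: "The effect of improved patient selection and the potential better cost-effectiveness of intensive management of early pSpA will be estimated".

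Goal 3 in section 5.2 speaks of the need for "biomarkers that can identify at baseline different pathogenic subsets that are associated with the (lack of) response to a TNFi". It does not mention the csDMARD arm.

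For symptom duration the protocol names a comparison between arms, in sections 6.2 and 13.2: "The interaction between treatment group and symptom duration as a continuous predictor will also be analyzed". The only other predictor analysis in those lists is "Exploration of clinical parameters that could be predictive for reaching (sustained) clinical remission and/or flare". That covers clinical parameters and names no treatment comparison.

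Two design features matter here:

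- Patients in sustained remission in either arm enter the drug-free phase. Section 5.1 says "all study treatments (both in the “csDMARD Step-up”-group and the “TNFi Induction”-group) will be stopped".
- Patients of either arm who are not in remission at week 24 receive golimumab. Section 6.1 says "blinded study medication will be interrupted and all patients will start open-label SC golimumab for an additional 36 weeks". Section 7.1 lets them enter Phase B later, at week 48 or 60.

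**The concern.** The sentence in 4.1 has a criterion and a conclusion. The criterion relates the marker to the outcome. The conclusion is about benefit from a strategy, which is the outcome under induction minus the outcome under step-up at a given marker level. The criterion does not bring in the randomised arm, so the conclusion does not follow from it.

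Two misreadings become possible:

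- **Prognostic marker taken as predictive.** Marker-positive patients do better whichever strategy they receive. They would be named as the ones to treat early, although their gain from induction is no larger than anyone else's.
- **Wrong direction.** Marker-positive patients have a poor outlook but gain from induction, and marker-negative patients do well on either strategy. Prediction of the outcome then points to the marker-negative patients, who gain nothing.

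What is at stake is the later statement about who should receive early induction, and any selection-based cost-effectiveness estimate built on it. No primary or listed secondary endpoint is involved.

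**Working it through.** **Inputs from the protocol.** 90 patients randomised 1:1, 45 per arm (7.1). Remission rates 20% v 50%, Fisher's exact test, alpha 5%, power of at least 80% (13.1). The protocol gives no figures for the biomarker analysis.

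**Assumptions.** Two-sided 5% tests, a binary marker present in half the patients, and the marker-specific rates shown below. Sample sizes of 60 and 45 stand for incomplete sampling.

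**1. The plan's own figure.** Enumerating Fisher's exact test at 45 v 45 with 20% v 50% gives power 81.5%. The stated figure reproduces, and this point does not depend on it.

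**2. Two questions, two contrasts.** Write p(arm, marker) for the probability of drug-free remission.

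- Prediction of the outcome, arms pooled: [p(T,+) + p(C,+)]/2 − [p(T,−) + p(C,−)]/2.
- Dependence of benefit on the marker: [p(T,+) − p(C,+)] − [p(T,−) − p(C,−)].

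The first can be large when the second is zero.

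**3. Purely prognostic marker, no treatment effect.** Rates are 50% (marker +) and 20% (marker −) in both arms.

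- Benefit: 50 − 50 = 0 and 20 − 20 = 0, so the interaction is 0.
- Pooled marker contrast: 50% v 20%.
- Probability that Fisher's test finds the association: 81.5% at 45 v 45 and 59.6% at 30 v 30 by enumeration. Simulation with a random marker split gives 83-84% at 90 patients, 62-63% at 60 and 49% at 45.
- The interaction test (Wald, risk-difference scale) is positive in about 5-6% at 90 patients, close to nominal.

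**4. Purely prognostic marker, equal benefit of 15 points in both marker groups.**

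| Rates −/+ on step-up; −/+ on induction | Pooled association | Association in TNFi arm only | Interaction |
|---|---|---|---|
| 5%/35%; 20%/50% | 88% | 50% | 6% |
| 5%/25%; 20%/40% | 56% | 25% | 6% |

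Restricting the analysis to the TNFi arm does not cure the problem.

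**5. Reversed case.** Marker + patients reach 10% on step-up and 40% on induction (benefit 30 points). Marker − patients reach 60% on either (benefit 0).

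- Pooled: marker + (10 + 40)/2 = 25%, marker − 60%.
- The association points to the group without benefit in about 91% of trials at 90 patients, 74-75% at 60 and 61-62% at 45.

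**6. What the interaction can deliver.** For the case in step 5 with 90/4 = 22.5 patients per cell, the standard error is √[(0.1×0.9 + 0.4×0.6 + 0.6×0.4 + 0.6×0.4)/22.5] = √(0.81/22.5) = 0.190. The true interaction is 0.30, so 0.30/0.190 = 1.58, and power is about 35%. The 95% interval is about ±1.96×0.190 = ±37 points. Simulation gives 34-36% at 90 patients, 26-27% at 60 and 22-23% at 45.

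**The case against.** The strongest reply is that 4.1 states an aim and not an analysis. It names no test, model, population or threshold, and it says only that patients may benefit. A reader might infer that the protocol prescribes a pooled association test without treatment arm, so that prognostic markers will be flagged at the rates above. The document does not support that. The model could be set in an analysis plan that is not shown. The rates belong to tests chosen here for illustration, and every marker-specific rate is assumed. A marker that predicts remission may also predict benefit. The defensible statement is that the stated inference can mistake prognosis for benefit.

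A reader might also take goal 3 as fixing a single-arm analysis. Its wording explains why biomarkers are wanted after the earlier proof-of-concept trial. It shows the same framing but specifies no analysis.

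A third inference would be that the whole health-economic evaluation is compromised. Goal 4 in 5.2 compares the early strategy with usual care and does not need a marker. Only the marker-based selection estimate in 4.1 is touched.

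Two further objections stand and shape the fix:

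- Because non-remitters of both arms receive golimumab from week 24, the drug-free remission contrast is partly early against delayed golimumab. It does not show how patients do on step-up alone.
- At 22-36% power, admitting only markers with a demonstrated interaction to the cost-effectiveness estimate would discard most truly predictive ones.

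What does not stand is that this is only missing detail. The sentence states an inference, and a plan that followed it would answer a different question from the one asked. The contrast with symptom duration does not show that an interaction for biomarkers was considered and rejected, but it does show that the protocol uses the right tool for a question of the same form.

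**Conclusion.** The point holds in a limited form. The aim in 4.1 infers benefit from early induction from prediction of an outcome that both arms can reach, and no treatment comparison by marker is named anywhere. That can lead to a prognostic marker being presented as one that identifies who benefits, or to the wrong group being selected.

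For a trial of 90 with a marker in half the patients, the illustrations give an association in about 56-88% of trials with the arms pooled, or 25-50% within the TNFi arm, for markers that do not modify benefit. The interaction test gives about 5-6%. The reversed case misleads in about 91%. These figures rest on assumed rates and are not forecasts for this trial. Severity is moderate: the work is exploratory and no primary figure changes, but the sentence should be corrected before it carries over into the analysis and the selection claim.

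**What to change.** Replace the sentence in 4.1 and align goal 3 in 5.2, for example:

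> Baseline markers of benefit from early induction will be explored through the treatment-by-marker interaction among all randomised patients with a sample. Outcomes are week-24 clinical remission, before any open-label golimumab, and drug-free remission, with patients who never enter Phase B counted as not reaching it. The induction-minus-step-up difference will be reported in each marker group with a 95% confidence interval. These analyses are exploratory. The drug-free remission contrast compares the randomised strategies, including later open-label golimumab in both arms. Markers associated with remission irrespective of arm will be described as prognostic. Any marker-based cost-effectiveness estimate will use arm-specific outcomes by marker group and carry their uncertainty.

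No significance threshold on the interaction should decide which markers enter the cost-effectiveness estimate. If the sponsor prefers not to make the comparison, the alternative is to remove the reference to benefit and call the markers prognostic.

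The cost is wording and a small extra analysis. Baseline research samples are already scheduled before treatment and irrespective of arm (11.4), so no patients or procedures are added. The downside is that the patient-selection claim becomes weaker and exploratory. With synovial sampling limited to three units (8.1), tissue markers may sit at the lower end of the power range.
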